3.2 Secondary Objectives

- To determine the safety and tolerability of SurVaxM in patients receiving standard care adjuvant temozolomide.
- To evaluate overall survival (OS) in patients with survivin positive newly diagnosed GBM treated with SurVaxM and adjuvant temozolomide.
- To describe the immune response in patients treated with SurVaxM and predictors of response.
- To evaluate objective tumor response rate (applicable only for patients with evaluable disease at study entry, as defined per RANO criteria (40)) and predictors of response.

[figure not shown]
4 METHODOLOGY

4.1 Study Design

This is a multi-center, open label, single arm, phase II trial in adult patients with newly diagnosed GBM, evaluating the efficacy and safety of SurVaxM and adjuvant temozolomide after patients have received concurrent radiation and temozolomide.

Patients will receive a postoperative MRI, within 96 hours of surgical resection, followed by ~4 weeks recovery time. Then they will receive 6-week duration of radiation therapy with temozolomide. A post-chemoradiation MRI will be performed within 1-28 days to ensure no tumor recurrence or progression.

Figure 8 Pre-Study Treatment and Imaging Requirements

[figure not shown]

HLA tests and tumor testing for survivin status can be performed at any time prior to vaccine priming, while the rest of screening assessments should be performed after completion of chemoradiation and prior to vaccine priming.

As shown in **Figure 8**, first priming administration of SurVaxM should occur within 7-28 days after completion of chemoradiation. Adjuvant temozolomide therapy (TMZ) will begin \geq 28 days after completion of concomitant temozolomide radiation therapy and given for 6 cycles or more (at the discretion of the investigator), or until intolerance or tumor progression.

Figure 8 Treatment Schema

SurVaxM should be administered approximately every 2 weeks (\pm 3 days) during the priming phase and then approximately every 12 weeks (\pm 2 weeks) during the adjuvant phase. Following completion or discontinuation of TMZ in the absence of progression, SurVaxM may be continued approximately every 12 weeks during the maintenance phase until intolerance or disease progression.

All participants will sign an informed consent prior to study related tests. All participants will meet the inclusion and exclusion criteria summarized in **Section 5.1** and **Section 5.2** Participants will be treated on an outpatient basis.

4.2 Target Accrual and Study Duration

The target accrual for this phase II trial is 50 evaluable patients with survivin positive newly diagnosed GBM. Approximately 2 patients per month will be enrolled, with follow-up of at least 12 months after the last enrolled patient. Patients will be followed until death to determine overall survival. The participants will initially receive treatment with radiation and chemotherapy with temozolomide as per standard of care. Thereafter, patients will receive SurVaxM and 6

cycles of adjuvant temozolomide (or more at the discretion of the investigator), until intolerance or tumor progression. Patients are eligible for treatment with SurVaxM until disease progression or unacceptable toxicity.

5 PARTICIPANT SELECTION

5.1 Inclusion Criteria

To be included in this study, participants must meet the following criteria:

- 1. Age \geq 18 years of age.
- 2. Have a Karnofsky performance status ≥ 70 (i.e. the patient must be able to care for himself/ herself with occasional help from others; refer to **Appendix B**).
- 3. Documented survivin-positive tumor status.
- 4. Pathologically confirmed diagnosis of glioblastoma multiforme (GBM). Or WHO grade IV [gliosarcoma]
- 5. Have the following clinical laboratory values obtained within 14 days prior to registration:
 - Absolute neutrophil count (ANC) $\geq 1.5 \times 10^9/L$
 - Platelets $> 100 \times 10^9/L$
 - Hemoglobin (Hgb) > 9.0 g/dL
 - Serum total bilirubin: $\leq 1.5 \text{ x ULN}$
 - ALT and AST < 4.0 x ULN
- 6. Patients on full-dose anticoagulants (e.g., warfarin or LMW heparin) must meet the following criteria:
 - No active bleeding or pathological condition that carries a high risk of bleeding (e.g., tumor involving major vessels or known varices)
- 7. Adequate renal function, as defined below:
 - Creatinine $\leq 1.8 \text{ mg/dl}$
- 8. HLA-A*02, HLA-A*03, HLA-A*11 or HLA-A*24 positive patients.
- 9. MRI (completed within 96 hours after surgery) documenting gross total resection consisting of no gadolinium enhancement; or subtotal resection consisting of linear enhancement with (or without) nodular gadolinium enhancement measuring no greater than 1 cm x 1 cm x 1 cm total volume or 100 mm² in cross sectional area.
- 10. No evidence of true progressive disease from the postoperative period to the post-chemoradiation period, based on changes in the neurologic exam, steroid use, or evident radiographic progression, according to RANO criteria (see **Appendix C**). Patients with increased or new gadolinium enhancement may continue on protocol if in the investigator's judgment that enhancement is likely due to pseuodoprogression. The use of correlative imaging studies (including PWI) or diffusion weighted imaging (DWI), and

- repeat imaging after an interval of 2-4 weeks is strongly encouraged to help distinguish between pseudoprogression and true progression.
- 11. Participants of child-bearing potential must agree to use adequate contraceptive methods (e.g., hormonal or barrier method of birth control; abstinence) prior to study entry and, have a negative pregnancy test prior to starting study treatment. Should a woman become pregnant or suspect she is pregnant while she or her partner is participating in this study, she should inform her treating physician immediately.
- 12. Dexamethasone dose less than or equal to 4 mg daily at time of study enrollment.
- 13. Patients must have completed initial radiation therapy (RT) and temozolomide (TMZ) for the treatment of their glioblastoma (i.e., completed 6-week course of RT and, completed ≥ 75% of 6-week course of induction TMZ chemotherapy).
- 14. Participant or legal representative must understand the investigational nature of this study and sign an Independent Ethics Committee/Institutional Review Board approved written informed consent form prior to receiving any study related procedure.

5.2 Exclusion Criteria

Participants will be excluded from this study for the following:

- 1. The patient must not have received any immunotherapy for their brain tumor.
- 2. Patients with serious concurrent infection or medical illness, which in the treating physicians opinion would jeopardize the ability of the patient to receive the treatment outlined in this protocol with reasonable safety.
- 3. Patients who are pregnant or breast-feeding.
- 4. Patients receiving concurrent therapy for their tumor (i.e. chemotherapeutics or investigational agents) other than temozolomide.
- 5. Patients with a concurrent or prior malignancy are ineligible unless they are patients with curatively treated carcinoma-in-situ or basal cell carcinoma of the skin. Patients who have been free of disease (any prior malignancy) for at least 3 years are eligible for this study.
- 6. Patients who have had repeat craniotomy for tumor therapy after receiving RT and TMZ treatment
- 7. Patients who received other chemotherapeutics or investigational agents in addition to their radiation therapy and concomitant temozolomide treatment.
- 8. Patients who have received Gliadel wafers or alternating electrical field therapy are not eligible for this study.
- 9. Known history of an autoimmune disorder.
- 10. Known human immunodeficiency virus (HIV) positivity or acquired immunodeficiency syndrome (AIDS) related illness or other serious medical illness.
- 11. Patients who have contraindication to MRI.

- 12. Unwilling or unable to follow protocol requirements.
- 13. Any condition which in the Investigator's opinion deems the participant an unsuitable candidate to receive study drug.
- 14. Received an investigational agent within 30 days prior to registration.

5.3 Inclusion of Women and Minorities

Both men and women and members of all races and ethnic groups are eligible for this study.

6 TREATMENT PLAN

6.1 Dosing and Administration

Treatment will be administered on an outpatient basis. Reported adverse events (AEs) and potential risks are described in **Section 1.9**. Appropriate dose modifications are described in **Section 6.2**.

Vaccine Priming Phase

Beginning 7-28 days after completion of standard chemoradiation therapy, patients will receive the first of four priming doses of SurVaxM in emulsion with Montanide with Sargramostim. Subsequent priming doses are given every other week (on priming Days 15, 29 and 43 ± 3 days) via subcutaneous injection. Patients will receive approximately 500 mcg SurVaxM in 50/50 volume emulsion with Montanide ISA 51 (1 cc total) and a second separate injection of 100 mcg sargramostim in close proximity (1-3 cm) to the first injection.

Adjuvant Temozolomide (TMZ) / Vaccine Phase

TMZ will begin no sooner than 28 days after completion of concomitant temozolomide radiation therapy and only when the absolute neutrophil count (ANC) is $\geq 1500/\mu L$ and the platelet count is $\geq 100,000/\mu L$.

TMZ will be dosed on days 1-5 of repeated 28-day cycles. A dose of 150 mg/m² body surface area per day will be given for the first cycle of TMZ. This dose will increase to 200 mg/m² body surface area per day in subsequent TMZ cycles, in the absence of Grade 3 and Grade 4 hematological toxicity and with adequate count recovery after the first cycle. Any change in weight of more than 10% will require re-calculation of the administered TMZ dose; otherwise, dosing may be based on the baseline weight. The total dose of TMZ shall be rounded to the nearest 10 mg increment. TMZ should continue for six cycles, or until intolerance or progression in accordance with RANO criteria.

Vaccine Maintenance Phase

Following completion or discontinuation of TMZ for reasons other than tumor progression, SurVaxM should be administered every 12 weeks (± 2 weeks) after the priming phase until intolerance or tumor progression.

6.1.1 Administration of SurVaxM

SurVaxM must be administered at the clinical trial site by appropriately trained staff.

SurVaxM injections must be performed using an appropriate needle for subcutaneous administration. A 23-gauge needle is recommended. Each dose of SurVaxM vaccine in emulsion with Montanide ISA 51 will be given in a total volume of 1.0 mL. Each dose will contain 500 mcg SurVaxM and will be administered subcutaneously. The location of each injection will be recorded. In addition, 100 mcg sargramostim will be administered subcutaneously as a second injection given in close proximity (1-3 cm) to the SurVaxM injection. The injection site should be administered on the opposite side of the body from the previous injection.

Injections over the deltoid muscle are preferred, and the site of administration should alternate between left and right arms for each successive treatment. Alternative sites, including the anterior thigh, may be used if necessary. SurVaxM injections should not be given to areas of skin with dermatologic conditions (such as persistent injection site reactions, infection, edema, or scarring) that will not allow easy access for study drug administration or evaluation of localized adverse events. If such conditions or other circumstances contraindicate injections as outlined above for an individual patient, alternate sites can be used, but this should be discussed with the Study Principal Investigator.

Following administration of SurVaxM, patients must remain in clinic for observation a minimum of one hour following each vaccination to evaluate and treat any potential immediate hypersensitivity reactions.

Measurement of Local Reaction: Measurement of any local reaction that may occur once the patient leaves the clinic will be performed by the patient or caregiver. At the time of injection, study staff should mark the outline of the injection site on the skin. Patients/caregiver will then be instructed by the study staff to measure the area of local reaction at its perceived maximum (using the diameter of a U.S. quarter – approximately 1 inch – as a reference standard), between 24-48 hours of administration of SurVaxM. Patients (or caregivers) will be asked to record the approximate dimensions of the reaction (if any) and the date it was measured. The study coordinator will contact the patient (or caregiver) within 3 to 5 days hr after the injection to obtain and record the patient's local reaction measurement.

6.1.2 Administration of Temozolomide

Temozolomide (TMZ) will be orally self-administered, or administered IV in the clinic, around the same time each day (in the evening) on days 1 through 5 of each cycle during the adjuvant phase. A dose of 150 mg/m² body surface area per day will be given for Cycle 1 of TMZ. This dose will increase to 200 mg/m² body surface area per day in subsequent TMZ cycles pending hematologic count recovery. Any change in weight of more than 10% will require re-calculation of the administered temozolomide dose; otherwise, dosing may be based on the baseline weight. The total dose of TMZ shall be rounded to the nearest 10 mg increment. Dosing should occur according to instructions in the product label and per standard practice, with consideration to the guidance outlined below (see **Section 6.2.2**). Patients who want to get their Temozolomide

locally and closer to home may do so by their oncologists. However, patients would still get their vaccine doses and disease assessments done at their enrollment site.

6.2 Dose Modifications

Every effort should be made to administer trial treatment on the planned schedule. In the event that individual patients experience treatment related toxicity, subsequent trial treatment may be delayed, omitted and/or discontinued as described below

6.2.1 SurVaxM Dose Omission or Discontinuation

Since all toxicities related to SurVaxM are expected to be immunologically mediated, no adjustment to the administered dose will be allowed.

If any unexpected significant toxicity (e.g., CTCAEv4 Grade 3) is observed, and there is a reasonable likelihood that the event may be associated with administration of SurVaxM and/or sargramostim, the next immunization for that patient should be withheld until the toxicity improves to mild severity or less. The immunization may be held for up to 2 weeks following the withheld dose. If significant toxicity is observed again or is not reversible, all further immunizations should be discontinued.

If vaccinations are discontinued for any reason, temozolomide administration may continue at the Investigator's discretion

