1.9 Risks and/or Benefits

1.9.1 SVN53-67/M57-KLH

Minor risks due to injection of SVN53-67/M57-KLH include:

- minor pain at the injection sites (common),
- local swelling of the subcutaneous tissues that may last several minutes to an hour (common)
- itching or redness at the injection site (common)
- infection is a possible risk of any injection (rare)

Major risks of SVN53-67/M57-KLH arise from the fact that although the survivin protein is rarely present in normal cells of the body, some normal cells could contain survivin making it possible that the vaccine could cause a reaction against normal tissues (autoimmunity). Patients will be observed for signs of such a reaction, using physical examinations and blood studies. A second major risk of treatment with SVN53-67/M57-KLH is that of a severe allergic or anaphylactic reaction. In the initial phase I clinical study, no allergic reactions or autoimmune phenomena were seen. All patients in this phase II study will be followed carefully for signs and symptoms of autoimmunity and allergic reactions.

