6.3.1 Guidance for Management of Expected Toxicity

6.3.1.1 Local Injection Site Reaction

Based on the experience with SurVaxM and other peptide vaccines, local injection site reactions are likely to be the most common event associated with the administration of SurVaxM. However, not all patients may experience an injection site reaction with the first few administrations of vaccines, and not all patients who experience injection site reactions may experience a reaction with every injection of vaccine. Erythema and pruritus occurred most frequently, but localized swelling, pain, rash, induration, bruising and urticaria are also possible, and may be relatively common. Some injection site reactions may extend for multiple centimeters into the surrounding dermis and take up to several days to resolve.

The clinical experience to date suggests that nearly all injection site reactions are tolerable and resolve without the need for intervention. Topical corticosteroids are permitted to treat injection site reactions at the discretion of the investigator. Nevertheless, systemic corticosteroids should be reserved for severe injection site reactions only since they may also compromise the immune response to the vaccine and could negate its effect. Topical or systemic non-steroidal anti-inflammatory agents (e.g. ibuprofen, naproxen, aspirin) or antihistamines (e.g. Claritin®, Allegra®, Benadryl) may be used as alternatives; however, routine use to prevent injection site reactions should be avoided, and doses should be the minimum necessary for appropriate clinical management.

SurVaxM injection sites should be rotated in accordance with the applicable study protocol; injections should not be given to areas with evidence of persistent local reaction.

Injection site reactions are considered adverse events and should be reported as such, using an appropriate descriptive term. (For example, "injection site erythema" should be used rather than the less descriptive term "injection site reaction".) **Section 10.1.2.1** provides guidance for the severity ratings of possible injection site reactions.

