6.3.1.2 Hypersensitivity Reactions

Hypersensitivity-like reactions could occur. Precautions should be taken to prepare for the possibility of anaphylactic/hypersensitivity reactions after SurVaxM/Montanide/sargramostim administration. Patients should be observed as per institutional standards, but for a minimum of 1 hour following each vaccination to evaluate and treat any potential immediate hypersensitivity reactions. The use of all routine supportive medication is permitted for hypersensitivity reactions, although routine use of prophylactic antihistamines, nonsteroidal anti-inflammatory agents and concomitant systemic corticosteroids are to be avoided if at all possible. If used, doses of steroids should be the minimum necessary for appropriate clinical management. If any new

administration of or increased dose of systemic steroids is necessary, every effort should be taken to taper, and preferably discontinue treatment with them, as quickly as clinically feasible.

For pain or fever, acetaminophen (325 mg tabs, 1 or 2 p.o. every 4 hours p.r.n.) will be utilized preferentially. Pretreatment of participants with acetaminophen may be instituted as warranted for a temperature of 38°C. Fevers lasting more than 8 hours after treatment will be evaluated in terms of potential infection. Aspirin, naproxen and ibuprofen are acceptable alternatives to acetaminophen for pain or fever, but are not preferred.

For mild to moderate local injection site pain that is unresponsive to acetaminophen, oral opiates will be used (oxycodone, 5–10 mg p.o. every 4 hours, p.r.n.). Pain that is of more than mild to moderate grade will be investigated for sources other than the therapy, and managed accordingly.

Anticonvulsant, antihypertensive and antidiabetic medications should be used as indicated. Antiemetics may be administered at the discretion of the treating physician.

For delayed hypersensitivity reactions, investigators should treat for symptomatic relief but avoid corticosteroid use whenever possible.

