10 SAFETY EVALUATION

10.1 Adverse Events

10.1.1 Definition

An adverse event or adverse experience (AE) is any untoward medical occurrence associated with the use of a drug in humans, whether or not considered drug related. Therefore, an AE can be ANY unfavorable and unintended sign (including an abnormal laboratory finding), symptom, or disease temporally associated with the use of a medicinal (investigational) product, whether or not considered related to the medicinal (investigational) product (attribution of 'unrelated', 'unlikely', 'possible', 'probable', or 'definite').

An AE is considered "unexpected" if it is not listed in the investigator brochure or is not listed at the specificity or severity that has been observed; or if an investigator brochure is not required or available, is not consistent with the risk information described in the general investigational plan in other study-related documents.

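### Section 6.2.1 requires SurVaxM to stop only if significant toxicity recurs or is irreversible, so nothing written as mandatory bars full-dose re-exposure after a first resolved anaphylaxis or related life-threatening event

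*Combined protocol and SAP*

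**What the plan says.** Section 6.2 opens with a general instruction: "Every effort should be made to administer trial treatment on the planned schedule". It then adds that treatment-related toxicity may lead to delay, omission or discontinuation, as set out in the subsections that follow.

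Section 6.2.1 is the subsection for SurVaxM. It allows no change to the administered dose. Its trigger begins "If any unexpected significant toxicity (e.g., CTCAEv4 Grade 3) is observed" and also needs a reasonable likelihood of association with SurVaxM and/or sargramostim. The action is to withhold the next immunization until the toxicity is mild or less, for up to two weeks. The permanent stop is: "If significant toxicity is observed again or is not reversible, all further immunizations should be discontinued".

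The risk is foreseen. Section 1.9.1 states: "A second major risk of treatment with SVN53-67/M57-KLH is that of a severe allergic or anaphylactic reaction". Section 6.3.1.2 asks sites to prepare for "the possibility of anaphylactic/hypersensitivity reactions after SurVaxM/Montanide/sargramostim administration" and requires at least one hour of observation after each vaccination. It gives treatment advice but no rule on holding, re-dosing or stopping. It sits under the 6.3.1 heading "Guidance for Management of Expected Toxicity".

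Section 10.1.1 calls an adverse event unexpected "if it is not listed in the investigator brochure or is not listed at the specificity or severity that has been observed".

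Other places limit treatment in general terms. Section 4.2 says: "Patients are eligible for treatment with SurVaxM until disease progression or unacceptable toxicity". Section 6.4 uses the same criterion. Sections 4.1 and 6.1 continue SurVaxM until intolerance or progression. Section 6.6 provides for withdrawal when the investigator considers it medically necessary, or by investigator decision.

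**The concern.** For an individual patient, the decision that matters most after a severe allergic reaction is whether to give the same product again. The protocol names this reaction as a major risk, yet its one graded vaccine rule describes hold and resume, with a mandatory stop only at a second event or if the first does not reverse. At stake is the safety of a patient who has had one such reaction and recovered. Whether that patient is re-exposed, at full dose, depends on how the local investigator reads general terms.

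The trigger adds a second uncertainty. A site could reasonably ask whether a reaction described under expected toxicity counts as unexpected for 6.2.1, and so whether even the hold applies.

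**Working it through.** The main check is a reading of the text. The plan states no figure on this point to reproduce.

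**1. Apply 6.2.1 to a first related anaphylaxis or Grade 4 event that resolves.**
- If it counts as unexpected: the next dose is withheld until the event is mild or less. Once it has resolved, the event has not been observed again and is not irreversible, so the permanent stop is not triggered.
- If it counts as expected: 6.2.1 supplies no hold. Section 6.3.1.2, where the reaction is discussed, supplies none either.
- On both branches no sentence requires vaccination to end. The two-week limit may imply a stop for a toxicity that resolves more slowly, but the text does not say so.

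**2. Look for a mandatory stop elsewhere.**
- 4.2 and 6.4: unacceptable toxicity, not defined by grade or event.
- 4.1 and 6.1: intolerance, also undefined; for SurVaxM it is attached to dosing after the priming phase.
- 6.6: medical necessity or investigator decision; the numbered withdrawal list has no toxicity item.
- 10.1.2.1: grades injection-site reactions but attaches no dosing action.
- 12.10: no early termination criteria.
- Section 11: the monitoring board reviews the study annually.

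None names anaphylaxis or Grade 4 as a reason to end SurVaxM. By contrast, Table 2 in 6.2.2 enters Grade 4 non-hematological toxicity under discontinuation of temozolomide, apart from alopecia, nausea and vomiting.

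**3. When the next dose would fall due.** Inputs: priming interval 14 ± 3 days (Table 3, footnote 1); later interval 12 ± 2 weeks (4.1, 6.1); hold of up to 14 days (6.2.1), counted from the scheduled date.
- After priming dose 1, 2 or 3: 14 − 3 = 11 to 14 + 3 = 17 days; with the full hold at most 17 + 14 = 31 days.
- After priming dose 4: 10 × 7 = 70 to 14 × 7 = 98 days; with the full hold at most 98 + 14 = 112 days.

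**4. What phase I can say about the risk.** Nine patients were treated (1.8.2) and no allergic reaction was seen (1.9.1). The exact one-sided 95% upper limit for 0 of 9 is 1 − 0.05^(1/9) = 0.283, about 28%. This shows how little nine patients can exclude. It is not an estimate of the rate.

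**The case against.** The strongest reply is that the protocol, read as a whole, already prevents re-dosing. Sections 4.2 and 6.4 make absence of unacceptable toxicity a condition of treatment, and few clinicians would call a life-threatening anaphylaxis acceptable. Section 6.2 itself qualifies the planned schedule when toxicity occurs. Network sites must report every serious event to the coordinating centre within one business day (Appendix A), so it would be known centrally well before the earliest next dose at 11 days. Sections 1.4.2 and 12.10 also cite reassuring experience with other peptide vaccines in Montanide and with another vaccine given with temozolomide.

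Much of this stands. The protocol permits the next dose; it does not order it. A reader might infer that sites would re-dose, or that the protocol directs them to; the documents support neither, because the discretionary stops are real. But the qualification in 6.2 refers the reader to the rules below it, and for SurVaxM those have no first-event stop. Central reporting conveys the event without saying what to do about the next dose. Experience with other products bears on how often a reaction occurs, not on what should follow one.

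A reader might also infer that anaphylaxis definitely falls outside the hold. That goes too far. Expectedness under 10.1.1 depends on the investigator brochure, which is not among the documents, and it is not certain that the adverse-event definition governs the word in a dosing section. The wording is unclear, and no more than that can be said.

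A further fair objection is that a stop after any Grade 4 event would be too broad. Section 1.4.4 lists severe cytopenias among the common Grade 3 to 4 effects of temozolomide, and 1.9.3 lists low counts with sargramostim. The stop should therefore exclude hematological events and say how a sargramostim first-dose reaction is handled.

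**Conclusion.** The point holds as a gap in a written safety rule. The only graded SurVaxM rule does not bar full-dose re-exposure after a first resolved anaphylaxis or related life-threatening event, and only undefined or discretionary stops stand in the way. Whether the hold itself covers hypersensitivity is unclear. The reading of the permanent stop rests on the text alone; the point about the hold rests partly on an investigator brochure that could not be seen.

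Its size is the window in step 3 of the working: during priming, a decision is needed within 11 to 17 days, or 31 at most. No event rate is claimed, and the 28% limit should not be read as one. No bias in six-month progression-free survival is claimed either; nothing in the documents would support it. The change should be made because the risk is one the protocol itself calls major and the remedy is small.

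**What to change.** Keep the hold paragraph in 6.2.1 and add:

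> The hold applies to Grade 3 or higher hypersensitivity reactions whether or not considered expected. All further immunizations are permanently discontinued after any anaphylaxis, or any Grade 4 non-hematological event, reasonably likely to be associated with SurVaxM (including its Montanide emulsion) and/or sargramostim. A sargramostim first-dose reaction (1.9.3) that is neither anaphylaxis nor Grade 4 does not by itself trigger permanent discontinuation.

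Add to 6.3.1.2 a cross-reference to 6.2.1 for holding, re-dosing and discontinuation.

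The management of injection-site ulceration in 1.9.2 is unaffected, since 10.1.2.1 grades ulceration as 3. Separating a first-dose reaction from anaphylaxis remains a clinical judgement, because 1.9.3 lists signs such as hypotension, flushing and shortness of breath. What changes is that the consequence of that judgement is fixed.

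The cost is four sentences at the next amendment, with no new visit or data item. The downside is that a patient stopped before dose four becomes unevaluable for the primary endpoint and is replaced under 12.9, which already allows up to 15 additional patients. Temozolomide may continue under 6.2.1.
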